10.1.7 CLINICAL MONITORING

All aspects of the study will be carefully monitored by the sponsor and its representatives for compliance with ICH GCP, applicable local and national regulations and legal requirements, and current standard operating procedures (SOPs).

The monitoring of this study will be performed by the sponsor's and/or CRO's CRAs in accordance with the principles of GCP as laid out in the ICH "Good Clinical Practice: Consolidated Guideline".

The CRA, as a representative of the sponsor, has an obligation to ensure site staff follows the protocol. In doing so, the study monitor will visit the investigator and site periodically as well as maintain frequent telephone and email contacts. The CRA will maintain current personal knowledge of the study through observation, review of study records and source documentation, and discussion of the conduct of the study with the investigator and staff. Further details will be described in the Monitoring Plan.

10.1.8 QUALITY ASSURANCE AND QUALITY CONTROL

A regulatory inspection of this study may be carried out by health authorities. In addition, the sponsor or EC/IRB may audit the study. Such inspections/audits can occur at any time during or after completion of the study. If an audit or inspection occurs, the investigator and CRO agree to allow the auditor/inspector direct access to all relevant documents and to allocate their time and the time of their staff to the auditor/inspector to discuss any findings or relevant issues.

Quality control (QC) procedures at the CRO will be implemented to ensure data recorded into the eCRFs are accurate. QC checks will be carried out on an ongoing basis and according to the relevant SOPs. Records of QC checks will be documented and available for review.

10.1.9 DATA HANDLING AND RECORD KEEPING

The study will utilize an EDC system with eCRFs and an ePRO system with an eDiary. Data will be processed using validated computer systems conforming to applicable regulatory requirements.

Study data will be entered into the eCRFs and source documents by the site staff as the study is in progress; data entered in the eCRFs should be consistent with the data recorded in the source documents. The eCRF data will be reviewed and source data verified by the CRA during monitoring visits as outlined in the Monitoring Plan. All corrections or changes made to any study data must be appropriately tracked in an audit trail in the EDC system. An eCRF will be considered complete when all missing, incorrect, and/or inconsistent data has been accounted for.

In addition to the EDC system, an ePRO system will be used by the study personnel and patients to record seizure and rescue medication data. The data collected through the ePRO system (eDiary devices) is considered as source data. Data will be transferred from the ePRO system to the clinical database on an ongoing basis. During the OLE, the eDiary will be replaced with a paper-based diary. Data collected on the paper-based diary is considered as source data and will be entered into the eCRF by the site. Patients will answer daily questions in the paper diary about seizure occurrence, but the eCRF will only capture data for days on which a seizure occurred.

Data handling will be detailed in the Data Management Plan.

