Study Week	8	11	23	35	47	60	73	86	99	112	125	138	151	164	165	170	
Informed consent							X ^I										
C-SSRS	-	X	X	X	X	X	X	X	X	X	X	X	X	X	X	X	X
Eligibility assessment	X																
Adverse events	-	X	X	X	X	X	X	X	X	X	X	X	X	X	X	X	X
Physical and neurologic (including non-dilated ophthalmic) examinations	-	X	X	X	X	X		X		X		X		X	X	X	X
Dilated ophthalmic examination ^A						X		X ^A		X ^A		X ^A			X ^A		X
Vital signs ^B	-	X	X	X	X	X		X		X		X		X	X	X	X
Weight, body mass index	-	X	X	X	X	X		X		X		X		X		X	X
Electrocardiogram (12-lead)	-	X	X	X	X	X				X				X	X	X	X
AUA Symptom Index	-	X	X	X	X	X		X		X		X		X		X	X
Concomitant medications	-	X	X	X	X	X	X	X	X	X	X	X	X	X	X	X	X
Pregnancy test ^C	-	X	X	X	X	X	X ^I	X		X		X		X		X	X
Clinical laboratory tests	-	X	X	X	X	X		X		X		X		X	X	X	X
QoL assessments (QOLIE-31)	-		X	X	X			X		X		X		X		X	X
Clinical Global Impression of Severity (CGI-S)	X		X	X	X	X	X	X	X	X	X	X	X		X	X	
Patient Global Impression of Severity (PGI-S)	X		X	X	X	X	X	X	X	X	X	X	X		X	X	
Collect eDiary, Issue/Training of paper diary ^D	X																
Collect and compliance check of completed paper diary and issue new paper diary		X	X	X	X	X	X ^I	X		X		X		X	X	return	return
PK blood samples (XEN1101) ^E	-	X				X				X				X			X
Study drug compliance check	-	X	X	X	X	X		X		X		X		X			X

Study Period	Open-label Treatment														Post-Tx Follow-up ^{F,G}		
Visit Number	8A*	9	10	11	12	13A	14A-TC ^I	15A ^I	16-TC	17	18-TC	19	20-TC	21	F1b	F2b	ET
Study Day	56±3	77±3	161±7	245±7	329±7	420±7	511±7	602±7	693±7	784±7	875±7	966±7	1057±7	1148±7	1155±3	1190±10	
Study Week	8	11	23	35	47	60	73	86	99	112	125	138	151	164	165	170	
Dispense study drug to patient	X	X	X	X	X	X	X ^H	X	X ^H	X	X ^H	X	X ^H				

*: Last day of double-blind treatment period. Patients entering the OLE will be dispensed 20 mg QD of XEN1101 and return their previous study drug.

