5.3 ADDITIONAL ELIGIBILITY CRITERIA

In addition to meeting all of the inclusion criteria and none of the exclusion criteria during screening, and despite being on an appropriate treatment regimen with current medications, patients must also meet all of the following criteria to be eligible to participate in the DBP:

- a) During the planned 8-week baseline period preceding the randomization visit (Visit 3), patients must have a documented seizure frequency of ≥ 4 focal seizures per 28 days on average.

Note: In cases of delayed randomization caused by the COVID-19 pandemic preventing patients from attending site visits, data obtained during the 56 days of electronic diary (eDiary) entries prior to randomization will be used to define the “baseline period”, for purposes of determining eligibility for randomization.

In order to establish baseline seizure count, the types of countable focal seizures to be included in the count will be:

- Focal aware seizures with motor signs,
- Focal seizures with impaired awareness, and
- Focal seizures that lead to generalized tonic-clonic seizures.

- b) eDiary was completed a minimum of 80% of all days (ie, ≥ 45 days) during the 8-week baseline period as evidence of adequate compliance.
- c) Patients should not be seizure-free for more than 21 consecutive days during the 8-week baseline period.
- d) Patient does not show retinal macular disease, or retinal pigment epithelium abnormality on the dilated ophthalmic examination prior to randomization.

ELIGIBILITY CONFIRMATION

To ensure enrollment of appropriate patients, The Epilepsy Study Consortium (TESC) may be consulted to assist in eligibility evaluation. TESC will review and approve seizure eligibility and classification for the first patient at each site at a minimum. Detailed instructions regarding TESC assistance are provided in the Study Operations Manual. TESC can be consulted at any point during the DBP enrollment phase to assist with eligibility determination.

CRITERIA FOR ENTERING THE OLE

In addition to meeting all of the entry criteria for the baseline and DBP, patients must also meet all of the following inclusion criteria and none of the exclusion criteria to be eligible to participate in the optional OLE:

Inclusion Criteria:

1. Be properly informed of the nature and risks of the study and give informed consent in writing.

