- AEs.
- Physical and neurologic examinations, including ophthalmoscopy.
- Vital signs.
- Weight and BMI.
- 12-lead ECG.
- AUA Symptom Index.
- QoL assessment (QOLIE-31).
- CGI-S.
- PGI-S.
- Concomitant medications, including any changes to AEDs.
- Site check of diary and study drug compliance.
- Urine pregnancy test for females of childbearing potential (if positive a serum pregnancy test will be performed).
- Clinical laboratory tests.
- Blood sample for PK analysis (XEN1101).
- Collect remaining study drug supply from patient.
- Return of paper diary.
- **CCI**

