9 STATISTICAL CONSIDERATIONS

A formal statistical analysis plan (SAP) will be developed and finalized before database lock and will describe the participant populations to be included in the analyses, and procedures for accounting for missing, unused, and spurious data. This section is a summary of the planned statistical analyses of the primary and secondary endpoints. Formal analysis of the DBP will be executed upon completion of that component of the study. Analysis of the OLE will be executed separately and upon completion of that component of the study.

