9.3 POPULATIONS FOR ANALYSES

The analysis datasets will include the following:

- **ITT:** All randomized participants who received at least one dose of IMP during the DBP, and provided at least one record of post-treatment seizure frequency during the DBP. Participants will be analyzed as-randomized.
- **Per Protocol:** Participants analyzed according to product and dose received during the DBP, who completed at least 80% of all diary records for a minimum of 4 weeks during the DBP, complied with at least 80% of expected IMP administrations during the DBP, did not withdraw consent, terminate for administrative issues, or were otherwise lost to follow-up during the DBP.

- **Safety:** All participants who receive at least one dose of IMP during the DBP, analyzed according to product and dose received.
- **OLE Efficacy:** All participants entering the OLE who receive at least 1 dose of IMP following the DBP and who provide at least 1 month of diary data in the OLE. Participants will be analyzed as-treated.
- **OLE Safety:** All participants entering the OLE who receive at least 1 dose of IMP following the DBP. Participants will be analyzed as-treated.

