9.4.2 ANALYSIS OF THE PRIMARY EFFICACY ENDPOINT(S)

The monthly (28 days) seizure rate will be calculated separately in the baseline and DBP as the total number of focal seizures reported \times 28 / the total number of days seizure information is available in that period. The countable seizures for the primary endpoint will include focal aware seizures with motor signs, focal seizures with impaired awareness with or without motor signs, and focal seizures that lead to generalized tonic-clonic seizures.

Percent change from baseline will be calculated as (post-treatment monthly [28 days] focal seizure frequency – baseline monthly (28 days) focal seizure frequency) / baseline monthly (28 days) focal seizure frequency, so that a more negative number will represent greater benefit.

Primary analysis to test the null hypothesis as described in [Section 9.1](#) is based on the ITT population. Since the endpoint of percent change from baseline in monthly seizure count tends to be not normally distributed, an analysis of covariance (ANCOVA) model for the ranks of monthly (28 days) focal seizure frequency percent change from baseline will be used as the dependent variable, with baseline monthly (28 days) focal seizure frequency rank, arm (placebo, 10 mg, 20 mg, 25 mg), region, and background use of CYP3A4 inducer medication included as factors.

Under the assumption of a monotonic dose response relationship (true effect for the higher dose is not worse than the lower dose), the null hypothesis (H_{0123} : $MPC_{plac} = MPC_{10mg} = MPC_{20mg} = MPC_{25mg}$) will be tested based on linear contrast for the least square means (with coefficient of -3, -1, 1, 3 for placebo and the 3 treatment levels of 10, 20, and 25 mg) within the framework of the ranked ANCOVA model. Since only a positive dose response trend is of interest to demonstrate treatment effect, a 1-sided test with significance level of 0.05 will be used.

If a significant result is achieved ($p < 0.05$) under H_{0123} , the study will be considered positive and at least one dose level of XEN1101 should be better than placebo.

After H_{0123} is rejected, further testing (with the same significance level of 0.05) will be performed to formally test the pairwise difference H_{03} : $MPC_{plac} = MPC_{25mg}$, H_{02} : $MPC_{plac} = MPC_{20mg}$ and H_{01} : $MPC_{plac} = MPC_{10mg}$.

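### In the open-label extension the eCRF records only seizure days, so the database as described cannot tell a confirmed seizure-free day from an unanswered diary day

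*Combined protocol and SAP*

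**What the plan says.** During baseline and the double-blind period (DBP), seizure data pass electronically from the eDiary to the clinical database (Section 10.1.9). In the OLE a paper diary replaces the eDiary and the site transcribes it. Patients still answer daily, but "the eCRF will only capture data for days on which a seizure occurred".

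Other provisions that bear on this:

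- Table 1b schedules the following at OLE visits: "Collect and compliance check of completed paper diary and issue new paper diary". The OLE early termination list in Section 8.1 includes "Site check of diary and study drug compliance". Neither says that the result is entered.
- Section 6.4 bases OLE compliance on capsule counts. For the DBP it also uses daily eDiary entries and sets an 80% threshold.
- Section 10.1.9 adds: "An eCRF will be considered complete when all missing, incorrect, and/or inconsistent data has been accounted for".
- Section 9.3 limits the OLE Efficacy population to dosed participants "who provide at least 1 month of diary data in the OLE".
- Section 9.4.2 divides the seizure count by "the total number of days seizure information is available in that period", but defines this only for baseline and DBP.
- Section 9 leaves to the SAP "procedures for accounting for missing, unused, and spurious data". Section 9.4.9 also sends OLE analyses there, and Section 10.1.9 sends data handling to the Data Management Plan.

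**The concern.** If only seizure days are entered, the absence of a record has two meanings: the patient reported no seizure, or did not answer. Two quantities depend on telling them apart.

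The first is the denominator of an OLE seizure rate. A rate per day with information, as used for baseline and DBP, needs a count of answered days, and the described eCRF data cannot supply one.

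The second is membership of the OLE Efficacy population. A patient with no seizure entries may have completed a seizure-free month, which is the best possible outcome, or may have returned an empty diary, in which case the patient does not belong in the set.

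Section 4.3 names maintenance of efficacy as a purpose of the OLE. If blank days were treated as seizure-free, any seizures on those days would be lost and the OLE rate could only move toward benefit. There is no concurrent control arm to offset that shift.

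**Working it through.** The plan gives no figure on this point to reproduce. The check has three steps.

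**1. Does any described safeguard separate the two kinds of day?**

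- The diary checks in Table 1b and Section 8.1 take place at the site; no resulting data field is described.
- The completeness rule and the queries (Sections 10.1.9 and 10.1.9.1) act on expected data. No record is expected for a day without a seizure, so a blank day raises no query.
- Source verification compares the eCRF with paper. Leaving out a non-seizure day follows the stated rule, so it is not a discrepancy.

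None of these separates them. The paper source does keep the distinction.

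**2. How far could a rate move?** The documents give no OLE completion rate, so the inputs below are assumptions:

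- blank OLE days are counted as seizure-free;
- change is measured against a baseline rate per day with information;
- seizure rates are equal on blank and answered days.

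Let B be the baseline rate per 28 days, t the true change and c the share of OLE days answered. Over D calendar days the recorded seizures are B(1 + t)/28 × cD. The calendar-day rate is therefore B(1 + t)c, and

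apparent change = (1 + t)c − 1.

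Take B = 10 per 28 days (Section 9.2) and t = −0.30, the planning value there for 20 mg, which is the OLE dose. The true OLE rate is 7.0.

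| c | Apparent OLE rate | Apparent change | Apparent change if t = 0 | True reduction that reads as 50% (1 − 0.5/c) |
|---|---|---|---|---|
| 0.95 | 6.65 | −33.5% | −5% | 47.4% |
| 0.90 | 6.30 | −37.0% | −10% | 44.4% |
| 0.80 | 5.60 | −44.0% | −20% | 37.5% |

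Incomplete baseline diaries do not alter this. Section 5.3 requires that the "eDiary was completed a minimum of 80% of all days", that is, at least 45 of 56. With 56 days answered, 20 seizures give 20 × 28/56 = 10.0. With 45 answered, 20 × 45/56 = 16.07 seizures are recorded, and 16.07 × 28/45 = 10.0.

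**3. How much diary time is involved?** OLE treatment runs from Day 56 to Day 1148, so 1148 − 56 = 1,092 days. To Visit F2b it is 1190 − 56 = 1,134 days. Table 1b has diaries collected at 11 scheduled visits after Visit 8A: 9, 10, 11, 12, 13A, 15A, 17, 19, 21, F1b and F2b. Visit 14A adds one only for re-entering patients.

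**The case against.** The strongest reply is that the protocol is not an eCRF specification. The sentence in Section 10.1.9 says which days have seizure data entered; it does not exclude a form for diary dates or for the result of the compliance check. The Data Management Plan was not available, and the document reviewed holds the protocol's statistical section but not the separate SAP that it promises. Either might settle the matter, and parts of the objectives and endpoints are redacted. This stands as a limit: the finding concerns the database as described. A SAP rule alone would not be enough, however, because it cannot identify blank days that were never entered.

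The size is also hypothetical, and the bias could run the other way. If every blank day were truly seizure-free, the calendar-day rate would be correct and an answered-day denominator would overstate the seizure rate: a true 7.0 would become 7.0/0.90 = 7.78 (−22.2%) at 90% completion and 7.0/0.80 = 8.75 (−12.5%) at 80%. This stands too, and is why both denominators should be reported. Choosing between them still requires knowing which days were blank.

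Third, entry required at least 4 focal seizures per 28 days and no seizure-free run longer than 21 days at baseline. Patients with no OLE entries may therefore be few, and entries spread over a month do show diary use. That narrows the population problem without removing it.

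Finally, OLE efficacy is uncontrolled, and Section 6.5.3 lets background antiepileptic drugs and neurostimulation change, so attribution to XEN1101 is already limited. Entering seizure days only is a deliberate saving of site effort. These points bear on severity; they do not remove the ambiguity.

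**Conclusion.** The concern holds and is minor. Followed as written, Section 10.1.9 yields an OLE database in which confirmed seizure-free days and unanswered days look the same. It can neither supply a count of days with information nor verify the one-month diary criterion for a patient without seizure entries. Actual bias cannot be estimated. The shift of 3.5 to 14 percentage points for a true −30% (from −33.5% at 95% completion to −44% at 80%) rests on the three assumptions stated with the calculation and on illustrative completion rates. Baseline, DBP and the primary endpoint are not affected, and the information remains recoverable from paper. Confidence is medium, because the Data Management Plan or SAP may already deal with the point.

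**What to change.** At each OLE site visit where a diary is collected, enter in the eCRF the diary's start and stop dates and the number or dates of unanswered days. Back-enter the same items from diaries already collected. In the SAP, define the OLE denominator and the one-month criterion by completed diary days, add a calendar-day sensitivity analysis, and report diary completeness by interval. If the Data Management Plan or SAP already provides this, a cross-reference in Section 10.1.9 is enough.

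The cost is one short form at up to 11 scheduled visits per patient, where the diary is already collected, with no new patient procedure. The burden is site data entry. Full back-entry means reviewing up to 1,092 on-treatment diary days per patient, or 1,134 to Visit F2b. The number of OLE patients is not given. If all of the approximately 300 randomized patients entered and completed the OLE, the on-treatment ceiling would be 300 × 1,092 = 327,600 diary days. Counting blanks when each diary is handed in avoids most of that later work.

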10.1.9.1 DATA COLLECTION AND MANAGEMENT RESPONSIBILITIES

Data will be entered using the EDC system (eCRFs) and ePRO system (eDiary) while the study is active. The ePRO system consists of a patient eDiary device for collection of daily seizure activity and daily use of rescue medications to treat seizures. Investigational site personnel and patients will be granted a secure username and password in order to enter, review or correct study data, as applicable. Site staff will not be permitted to alter data entered by patients in the eDiary. A patient's personal seizure diary or study approved back-up paper diary may be used to supplement missing eDiary data only for missing days related to a documented temporary technical issue with the patient's eDiary and may not be used to correct poor patient compliance. The eDiary is the primary source and if the temporary issue is solved and data from the eDiary is available, data from the back-up paper diary will not be used. All passwords will be strictly confidential. These procedures must comply with appropriate regulations. During the OLE, the eDiary will be replaced with a paper diary.

Data collection is the responsibility of the investigational staff at the site under the supervision of the site investigator. The investigator is responsible for ensuring the data collection and study documentation comply with the ALCOA+C principles, and the timeliness of the data reported. Good Documentation Practices (GDP) should be followed to ensure all source documents are attributable, legible, contemporaneous, original and accurate (ALCOA), plus complete, consistent, endurable (ie, retrievable and readable after archiving), and available (+C), to ensure accurate interpretation of data.

Validation checks programmed within the database, as well as supplemental validation performed via review of the data listings, will be applied to the data in order to ensure accurate, consistent and reliable data. Data identified as erroneous, inconsistent, incomplete or inaccurate, or data that are missing, will be referred to the site for resolution through data queries where applicable. An eCRF will be considered complete when all missing, incorrect, and/or inconsistent data have been accounted for.

The eCRFs must be reviewed and signed by the investigator (or designee) who signed the protocol.

External study data collected outside of eCRFs such as clinical laboratory data and PK data will be sent to the sponsor's data management team for reconciliation and integration. Any discrepancies will be referred to the site for resolution through queries.

For medical information, the following thesauri will be used:

- Latest version of the MedDRA for medical history and AEs; and
- World Health Organization Drug Dictionary (WHODD) (2018 or higher) for prior and concomitant medications.

Data management processes, including data management and validation, will be outlined in the Data Management Plan.

10.1.9.2 STUDY RECORDS RETENTION

Patient records (including Electronic Medical Records [EMR]), source documents, monitoring visit logs, eCRFs, inventory of IMP, study and regulatory documents, and other sponsor correspondence pertaining to the study must be kept in the appropriate study files at the site. Source data is defined as all information in original records and certified copies of original records of clinical findings, observations, or other activities in a clinical study necessary for the evaluation and reconstruction of the clinical study. Source data are contained in source documents (original records or certified copies). These records should be retained in a secure file by the investigator according to the specifications in the ICH guidelines, relevant regulations, or as specified in the Clinical Trial Agreement, whichever is longer. Prior to transfer or destruction of these study records, Xenon must be notified in writing and be given the opportunity to further store such records. If the study records no longer need to be retained, it is the sponsor's responsibility to inform the investigator.

If the investigator relocates, retires, or for any reason withdraws from the study, the sponsor should be prospectively notified. The study records must be transferred to an acceptable designee, such as another investigator, another institution, or to Xenon.

Canadian federal law requires all records created during the conduct of a clinical trial be retained for 25 years under Division 5 of the Health Canada Food and Drug Regulations. The US Food and Drug Administration (FDA) requires all such records to be retained for 2 years following the date a marketing application is approved for the drug in the indication for which it is being investigated, or 2 years after the investigation is discontinued and FDA notified. Requirements in the European Union require these records to be retained for 15 years after completion or discontinuation of the trial or for at least 2 years after the last approval of a marketing application in the region.

